16.5 Device Deficiencies

All device deficiencies of the study device and Medtronic IN.PACT™ Admiral™ DCB must be documented on the CRF and reported to Sponsor, preferably within 24 hours of knowledge of the event. Reporting of device deficiencies includes reporting malfunctions, use errors, and inadequacy in the information supplied by the manufacturer including labeling. Documentation of device deficiencies on the CRF is sufficient for Sponsor reporting. However, if the CRF cannot be completed within the specified timeframe, reporting to the Sponsor can be completed via email or phone. In the event of a device deficiency relating to the study device, return the suspected device to the Sponsor for analysis. All device deficiencies will be reported to regulatory authorities as required and included in the clinical results (e.g., final report).

If the investigator or site staff becomes aware of death or any SAE suspected to be attributable to device deficiencies of the study device or Medtronic IN.PACT Admiral™ DCB, the principal investigator shall immediately notify the Sponsor and the IRB. In such cases, the principal investigator shall provide additional relevant information upon the request of the Sponsor, the head of the medical institution, or the IRB.

17. PROTOCOL DEVIATIONS

A protocol deviation is defined as an instance(s) of failure to follow, intentionally or unintentionally, the requirements of the protocol. The Investigator is not allowed to deviate from the protocol except:

- With prior approval from the study Sponsor, and the local IRB if applicable, or
- Under emergency circumstances to protect the rights, safety and well-being of the subjects, or

- Inadvertent protocol deviations (e.g., missed lab test) or deviation outside the control of the Investigator/site (e.g., subject does not show up for a scheduled follow-up visit, etc.), are not expected to have prior Sponsor approval;

All deviations must be documented separately on a CRF. Documentation of the deviation should include a description of the deviation, the reasons thereof. Protocol Deviations should be reported to the Sponsor and reviewing IRB according to their requirements. If the investigator has failed to comply with the protocol to eliminate immediate hazards to subjects or for other inevitable medical reasons the investigator shall document the deviation and immediately report it to the Sponsor and head of medical institution. Documentation of the Protocol Deviation on the CRF is sufficient for Sponsor reporting, however if the CRF cannot be completed within the specified timeframe, reporting to the Sponsor can be completed via email or phone.

The Sponsor may implement measures to reduce the number of deviations such as, but limited to, a site Corrective Action Preventive Action plan (CAPA), protocol amendment or additional site training. Repeated and serious non-compliance by the site that is not adequately addressed by the PI or his/her staff may lead to corrective action taken by Sponsor including requesting the site's withdrawal from the study.

18. STUDY EXIT

Active subject participation is expected to last for a maximum of 6 months. The Study Exit CRF must be completed when a subject exits the study early or completes the required follow-up visits. Reasons for exiting the study include, but are not limited to the following:

- **Subject Lost to Follow-up:** If a subject fails to comply with the Protocol requirements to attend the follow-up visit, the study site should make at least three (3) documented attempts to contact the subject and/or family or emergency contact and send a letter to the last known address of the subject by traceable mail before considering the subject lost to follow-up.
- **Voluntary Withdrawal:** A subject may voluntarily withdraw from the study at any time. If the subject had an adverse event, where possible, the subject should be followed until the resolution of the adverse event.
- **Investigator Withdrawal:** An Investigator may withdraw a subject for reasons, which may include failure to keep appointments, termination or cancellation of the study by the Sponsor, etc.
- **Study Completion:** This will be after the last scheduled follow-up visit has occurred as defined by the Protocol or subsequent amendments.
- **Death:** The Adverse Event CRF must also be completed.
- **Other:** Includes other possible reasons for exiting the study which may not be outlined above, as determined by the Sponsor or Investigator.

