14. FOLLOW-UP

The following sections describe follow-up requirements for all enrolled subjects in the KAIZEN study. All follow-up assessments and visits must be performed by someone who is study-trained and delegated to perform study follow-up.

- If the subject is seen by the Investigator between scheduled follow-up visits (i.e., not a study required assessment or visit), the assessment/visit should not be recorded on an CRF. However, if any adverse events are noted, an Adverse Event (AE) CRF needs to be completed for each event.
- If a revascularization occurs, images are required to be submitted for CEC review. The subject will still be required to return for the next scheduled follow-up visit if the unscheduled visit is out of the compliance follow-up window.

14.1 30-Day In-hospital Follow-up Visit or Telephone Follow-up Assessment

All Enrolled / Enrolled and Treated subjects are required to have a follow-up assessment occur at 30 days (+14 days) after enrollment. The 30-Day assessment can be an in-hospital follow-up visit or may occur by telephone assessment.

Refer to **Table 7** for 30-Day In-hospital Follow-up Visit or Telephone Follow-up Assessment data collection requirements.

14.2 6-Month Follow-up Visit

All Enrolled subjects are required to have a 6-Month (+30 days) Follow-up assessment phone call or in-hospital visit to monitor for adverse events.

All Enrolled and Treated subjects are required to have a Follow-up assessment occur at 6-Months (+30 days) after clinical trial treatment. The 6-Month visit must be an in-hospital visit.

Refer to **Table 7** for 6-Month Follow-up Visit data collection requirements.

All subjects will be exited from the study following the 6-month Follow-up visit.

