16.4 Reporting Adverse Events and Follow-Up

Adverse events should be reported throughout the subject's participation in the trial and not only at study mandated visits. Any subject who has unresolved adverse events at the end of their study participation will continue to be followed by the investigator per their standard of care. Source documents should be submitted to the Sponsor for review of the Adverse Event. Prior to submission to the Sponsor the source documents are to be appropriately redacted to remove the subject's name, and any other identifying information and the subjects unique Subject ID should be inserted on every page.

All adverse events, including subject deaths, must be reported on the AE CRF. In the event an adverse event cannot be submitted through the electronic database in a timely fashion, submission may be made to the Sponsor via email to [REDACTED] This does not replace the EDC reporting system; however, all information must still be entered in the EDC system as soon as feasible.

All efforts should be made to notify the Sponsor as soon as possible after first learning of an SAE. Additional information, obtained after the initial SAE, must also be reported as soon as possible to the study Sponsor. Deaths must be reported on the Study Exit CRF. If available, a copy of death records, medical records for the events that led to the subject's death, death

certificate and an autopsy report must be sent to the Sponsor as soon as they become available. Adverse event information will be collected up until each subject's study exit or study completion.

All AEs will be reviewed by the Sponsor and determined whether the AE meets regulatory reporting requirements. These events will be reported to the country's regulatory authorities according to the requirements of the country by the Sponsor or designee. The Investigator is responsible for reporting to the IRB, as applicable. In cases where the CEC does not agree with the Investigator's final assessment/classification of an adverse event, the Sponsor shall communicate both opinions to the regulatory authorities, if applicable.

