### **7.7.8 Adverse Event (AE) Rates**

Adverse event rates will be assessed on a subject level for the mITT and FAS. All site reported and CEC adjudicated reportable adverse events specified in the protocol will be included in the analysis. Adverse events

are collected starting at enrollment through subject exit from the study. Adjudicated AEs will be summarized by AE term and overall for number and percent of subjects experiencing each event, and number of events.

Adverse events summaries will be provided for the time-points of enrollment to 30 days, and 31 days to study exit in the following groups:

- Serious Adverse Event (SAE): Any AE that the CEC has determined meets the protocol definition of serious
- Adverse Device Effect (ADE): Any AE the CEC has determined meets the protocol definition of related to the use of the OAS
- Serious Adverse Device Effect (SADE): Any ADE that the CEC has the protocol definition of serious
- Unanticipated Serious Adverse Device Effect (USADE): Any SAE that the CEC has determined that by its nature, incidence, severity or outcome has not been identified in the current version of the risk analysis report

Any events for which the determination of seriousness and/or relatedness to the device cannot be determined by the CEC will count as serious and/or related for the purposes of this analysis.

In addition, a subject data listing of all reportable AEs will be presented from the time of enrollment to study completion and will include the following: adverse event term, AE onset date, days to event, seriousness, relationship to OAS and procedure, outcome, and date resolved (if applicable).

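### An investigator may withdraw a subject for missed appointments without the contact step that loss to follow-up requires, and event collection then stops, so reachable 6-month safety outcomes can be lost

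*Protocol*

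**What the plan says.** Protocol section 18 lists the reasons for leaving the study. Under Investigator Withdrawal it says: "An Investigator may withdraw a subject for reasons, which may include failure to keep appointments". Two other routes in that section carry a safeguard. Before a subject is classed as lost to follow-up, "the study site should make at least three (3) documented attempts to contact the subject and/or family or emergency contact", and a traceable letter must also be sent. Under Voluntary Withdrawal: "If the subject had an adverse event, where possible, the subject should be followed until the resolution of the adverse event". Investigator Withdrawal has neither step.

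Exit ends event collection. Protocol section 16.4 states: "Adverse event information will be collected up until each subject's study exit or study completion". SAP section 7.7.8 says adverse events "are collected starting at enrollment through subject exit from the study".

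For the 6-month contact, Protocol section 14.2 asks for a "Follow-up assessment phone call or in-hospital visit to monitor for adverse events" for all Enrolled subjects. For Enrolled and Treated subjects it adds: "The 6-Month visit must be an in-hospital visit". Note 10 to Table 7 names the telephone option only for subjects with a guide wire complication on entry or no device insertion.

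SAP section 7.7.7 analyses MAE as time to event and reads the 6-month rate at day 210. SAP section 7.7.8 reports adverse events as number and percent of subjects.

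**The concern.** The study treatment is a single procedure, finished long before any follow-up visit. Withdrawing a subject for missed appointments therefore changes nothing about treatment; it only stops data collection.

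The subjects affected may not be a random subset. Someone revascularized at another hospital, or unwell after an event, may be less likely to attend. In the MAE analysis a withdrawn subject would ordinarily be censored at exit, which is unbiased only if missing visits is unrelated to TLR or amputation. In the adverse event tables, a withdrawn subject left in the denominator counts as event-free after exit. Either way the 6-month safety rates could be understated in a single-arm study meant to supply safety data for commercialization in Japan. With few events expected among about 62 subjects, each unknown outcome is visible in the rate.

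**Working it through.** **1. The routes in Protocol section 18 that can follow a missed visit.**

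| Route | Contact step before exit | Follow-up after exit |
|---|---|---|
| Lost to follow-up | Three documented attempts plus traceable letter | None stated |
| Voluntary withdrawal | None stated | Existing adverse event followed to resolution where possible |
| Investigator withdrawal (missed appointments) | None stated | None stated |

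The same missed visit can thus lead to exit through a route with no contact requirement. Section 16.4 has unresolved adverse events followed under standard of care after participation ends, but does not provide for recording new events.

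**2. What is lost.** Only events after exit. For MAE these are major amputation and clinically-driven TLR up to day 210. Deaths after day 30 are not MAE events, although they remain reportable as serious adverse events. The primary endpoint is assessed at the procedure and is unaffected.

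**3. The denominator.** The plan's primary analysis size is 62 (Protocol section 9.1.5, Table 5): performance goal 0.50, anticipated rate 0.70, one-sided alpha 0.025, power 0.90. The normal approximation with null and alternative variances reproduces it:

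n = [(1.960 × √(0.5 × 0.5) + 1.2816 × √(0.7 × 0.3)) / 0.20]² = [(0.980 + 0.587) / 0.20]² = 61.4, rounded up to 62.

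**4. Unknown part of the 6-month rate.** With m subjects exited early and event-free to that point, the rate lies between x/62 and (x + m)/62, where x is the number of observed events. The width is m/62.

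- m = 1: 1/62 = 1.6 points
- m = 2: 2/62 = 3.2 points
- m = 4: 4/62 = 6.5 points

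**5. Illustration with 2 observed MAEs and 3 early exits (both assumed).**

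- Counted event-free: 2/62 = 3.2%
- Excluded, or censored at once: 2/59 = 3.4%
- All three had events: 5/62 = 8.1%

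**6. Illustration of informative loss (all inputs assumed).** Take 6 exits, a 10% rate in those who stay and 30% in those exited.

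- True rate: (56 × 0.10 + 6 × 0.30)/62 = 7.4/62 = 11.9%
- Censored analysis: 10.0%
- Counting the six as event-free: 5.6/62 = 9.0%

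The understatement is 1.9 points (censored) or 2.9 points (event-free). No withdrawal rate, MAE rate or link between missed visits and events is visible in the documents, so steps 5 and 6 show scale only.

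**The case against.** The strongest reply is that the plan already handles missed visits. The lost-to-follow-up route is written for exactly this case, Protocol section 17 treats a no-show as a deviation outside the site's control, and section 16.4 wants events reported throughout participation and not only at visits. The withdrawal clause is permissive. This stands as a limit on reach: a site may well use the better route. It does not remove the gap, because nothing obliges the site to do so before withdrawing the subject.

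Four stronger readings are tempting, and the documents do not support them.

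- **That 6-month outcomes will be lost.** The text permits the loss; it does not require it.
- **That a missed 30-day contact is the main danger.** That contact may already be by telephone, so a subject who misses it is not clearly one who could be reached that way. What remains is mainly the treated subject who misses the 6-month hospital visit, and by then most of the period has been observed.
- **That telephone follow-up is plainly closed to treated subjects.** Section 4 makes Enrolled and Treated a subset of Enrolled, so section 14.2 can be read as giving them the telephone contact plus a hospital visit. Note 10 to Table 7 points the other way. The text is ambiguous.
- **That investigator withdrawal should be abolished.** Section 11.3 has subjects told that the investigator may withdraw them in their best interest, and sections 18 and 19 provide for termination by the sponsor. Those grounds must remain.

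It is also fair that the bounds above apply to any attrition, that secondary endpoints carry no hypothesis tests (Protocol section 25.4.3), and that SAP section 7.1 tabulates discontinuation reasons and visit compliance, so such losses would be seen. Seeing them does not recover the events. The detail of SAP section 6.3 on missing data is not visible, and no claim is made about it; no analysis rule can restore events that were never collected.

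**Conclusion.** The concern holds as a modest, inexpensive improvement. Protocol section 18 allows exit for missed appointments without the contact step required for loss to follow-up, and both documents stop event collection at exit. Later clinically-driven TLR, major amputation and reportable adverse events can therefore be lost in a subject who is still reachable.

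The size is up to 1.6 points of the 6-month rate per subject on a base of 62, taking the mITT set at its planned minimum. How many subjects would be affected is unknown. Bias, as opposed to imprecision, further requires that missing visits be related to the events. A reader might infer that the primary result or the sample size is threatened; neither is, because Acute Device Success is settled at the procedure.

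**What to change.** In Protocol section 18, remove missed appointments from the Investigator Withdrawal reasons, keeping best-interest withdrawal and sponsor termination. Add that:

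- a missed visit is recorded as a protocol deviation and is not in itself an exit;
- the existing three attempts and traceable letter apply;
- an Enrolled and Treated subject who misses the 6-month hospital visit is contacted by telephone for MAE and adverse event status, unless consent has been withdrawn;
- records and images are retrieved for Clinical Events Committee (CEC) adjudication of any revascularization reported this way, since clinically-driven TLR needs angiographic confirmation.

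Align section 14.2 and note 10 to Table 7 so that the telephone fallback for treated subjects is explicit.

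The cost is a short protocol amendment, a few calls and some record retrieval. The sample size does not change. Telephone contact will not recover duplex patency, so that endpoint stays missing for these subjects.

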19. STUDY TERMINATION

This study may be suspended or prematurely terminated if there is sufficient reasonable cause. Written notification, documenting the reason for study suspension or termination, will be provided by the suspending or terminating party to study Principal Investigators and applicable reviewing bodies. If the study is prematurely terminated or suspended, the Principal Investigator will promptly inform the IRB and will provide the reason(s) for the termination or suspension.

Circumstances that may warrant termination include, but are not limited to:

- Determination of unexpected, significant, or unacceptable risk to subjects
- Insufficient adherence to protocol requirements
- Data that are not sufficiently complete and/or evaluable
- Sponsor management decision to discontinue the study

20. STUDY RESPONSIBILITIES AND MANAGEMENT

20.1 Conduct of Study

The study shall be conducted in accordance or compliance with the:

- Protocol;
- Study agreement;
- Conditions of approval imposed by the IRB
- Ethical principles that have their origin in the Declaration of Helsinki;
- Any local or national regulations, as appropriate, including ICH E6: Good Clinical Practices (GCP) and Ordinance 36: Ministerial Ordinance on Good Clinical Practice (GCP) for Medical Devices

The study cannot begin until approval from the Sponsor, applicable IRB, and regulatory authorities are obtained. In addition, appropriate insurance for the study to cover the cost of treatment of subjects in the event of a study-related injury, will be obtained prior to the start of the study, according to Japan requirements.

20.2 Investigator Selection and Responsibilities

20.2.1 Investigator Training

All treating physicians must be experienced in peripheral artery treatment (e.g., balloon angiography, stenting, atherectomy, etc.). The Sponsor will be responsible for ensuring that physicians are properly trained in the use of the CSI Peripheral OAS and on the protocol prior to enrolling subjects in this study. Training will be performed by qualified personnel from the Sponsor or designee.

Each investigator must complete at least one (1) roll-in. This will ensure proper device training, and procedural and data collection adherence. Up to three (3) roll-in subjects per Investigator (Principal Investigator and/or Sub-Investigator) are permitted. Roll-in subjects will be consented and followed per protocol, and their data will be reported separately.

20.2.2 Investigator / Investigational Site Delegation

Only site personnel delegated in writing by the Investigator will conduct study-related functions. All individuals delegated study-related functions must have documented training, at a minimum, on the study protocol.

20.2.3 Investigator Responsibilities

The Principal Investigator (PI) is responsible for protecting the rights, safety, and welfare of study subjects. In addition, the Investigator is responsible for:

- Providing agreement on the content of the protocol and conduct the study in compliance with the protocol and applicable regulations
- Providing adequate oversight of all study-related activities
- Maintaining control over the investigational devices, ensuring the devices are used solely by authorized users under his or her direct supervision, tracking the receipt and disposition of all study devices, and returning all devices upon the completion of termination of the study
- Disclosing financial, or other information, that may constitute a potential conflict of interest
- Maintaining source documents throughout the study and making them available/ providing direct access as requested during monitoring visits, audits/inspections, and IRB review
- Providing a current signed and dated curriculum vitae (CV). If any changes affecting the PI's qualification, an updated CV is required to be sent to the Sponsor
- Avoiding improper influence on, or inducement of the subject, monitor and Sponsor or other parties participating in, or contributing to, the study by complying with the informed consent process for the subject, study agreements and IRB approval of the study
- Obtaining IRB approval of the protocol, ICF and any other study-related documents prior to enrolling subjects. The Investigator will also be responsible for notifying the Sponsor within five (5) working days of becoming aware of the IRB withdrawing their approval of the study.
- Explain the appropriate use of the investigational devices to each subject.

- If a subject is receiving treatment by another primary physician, the investigators etc. shall inform the primary physician, with prior consent of the subject, that the subject will participate in the clinical trial.
- The head of the medical institution and the investigators etc. shall beforehand take necessary measures to ensure that adequate medical care is provided to a subject for any adverse event.
- The investigator shall promptly notify the subjects if the study is prematurely terminated or suspended and shall provide appropriate medical care to the subjects and take other necessary measures.
- The investigators etc. shall inform subjects of the fact that medical care is needed for adverse event(s) of which the investigator becomes aware, if applicable.
- Upon completion of a clinical trial, the investigator shall report the completion in writing and submit a written summary of the trial's outcome to the head of the medical institution.

The Investigator for each site may not begin enrollment until Sponsor receives and approves (when necessary) required documents, including a signed Study Agreement, IRB protocol and ICF approvals.

It is acceptable for the Investigator to delegate study-related functions to an associate or Sub-Investigator or trained Study Coordinator; however, the Investigator remains responsible for the proper conduct of the clinical investigation, including obtaining and documenting proper study informed consent, collecting all required data, submitting accurate and complete CRFs, maintaining applicable study records, etc.

At each site, appropriate procedures must be followed to maintain the security and confidentiality of individually identifiable health information, and will comply with all applicable health information confidentiality laws and regulations, including as applicable, the U.S. HIPAA Standards for Privacy of Individually Identifiable Health Information, Title 45 of the U.S. Code of Federal Regulations, Part 160 and 164, and the applicable health information privacy laws of any state or foreign jurisdiction (including Japan's Act on the Protection of Personal Information and applicable circulars published by Japan's Ministry of Health, Labor and Welfare. Each site may have its own internal procedures or requirements for use and release of subject medical information in research studies. Each Investigator is responsible for obtaining appropriate approvals, consents, or releases of medical information as dictated by their relevant subject privacy laws.

